In further analyses, putative covariates will be added to the model to examine whether the intervention remained statistically and clinically associated with cessation after controlling for the potential covariates. Each covariate considered for inclusion will be examined individually for a relationship with cessation outcomes. In the second step, those variables with a p value < .25 will be included in an initial model. Next, the potential confounder variable in the initial model with highest p value will be removed and the model will be run again. If the removal of the potential confounder variable does not result in a significant reduction in model fit (as indicated by a change in the model -2 log likelihood), then the variable is removed from further steps. The removal and subsequent testing of change in model fit will be repeated until all non-significant potential confounders are tested. Potential covariates include demographic variables (i.e., age, income, education), nicotine dependence score, depression score, body mass index, perceived stress, social smoking influences, *social ties, neighborhood cohesion, neighborhood smoking prevalence, neighborhood stress*, and time dependent covariates of self efficacy, spiritual well-being, social support, and *cessation resources*.

The magnitude of intervention effect sizes (e.g., differences in 7-day point prevalence proportions between TX and C groups, and odds ratios for cessation) will be estimated using 95% confidence intervals (95%CI). Effect size estimates allow evaluation of the "clinical" or practical significance/relevance of the study findings.

Analyses for Secondary Aims.

Aim #2. To evaluate the effect of the *Sister-to-Sister* intervention on individual (self-efficacy, spiritual well-being), interpersonal (social support), and neighborhood (cessation resources) factors and to determine if these factors mediate the effect of treatment on smoking cessation outcomes.

Hypothesis 2.1: As compared to the control group, women receiving the *Sister to Sister* intervention will have greater improvement in individual factors (self-efficacy, spiritual well-being), interpersonal factors (social support), and neighborhood factors (*cessation resources*) at 6-and 12 months.

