Hypothesis 2.2: Positive changes in individual factors (self-efficacy, spiritual well-being), interpersonal factors (social support, and neighborhood factor (*cessation resources*)) will mediate the effect of the 6- and 12-month cessation outcomes in women receiving the *Sister to Sister* intervention.

A generalized linear mixed models (GLMM) approach, as described for the Primary Aim, will be used for Aim 2. To examine the effect of treatment (TX vs C) on individual factors (self-efficacy, spiritual well-being), interpersonal factors (social support), *and neighborhood factors (cessation resources)* [Hypothesis 2.1], each of the individual variables within the factors will be used individually as the outcome (dependent) variables in the GLMM. As described above, treatment and measurement time will be considered fixed effects, and neighborhood will be

considered a random effect, with a *pair-specific fixed intercept parameter* to represent each neighborhood pair. Additional covariates, as described above, will be added to the model to determine the effect of treatment on these outcomes adjusted for the effect of the covariates.

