The analyses for Hypothesis 2.2 address the question of whether the individual (self-efficacy, spiritual well-being), interpersonal (social support), and neighborhood factors (cessation resources) explain (mediate) the relationship between the outcome (6- and 12-month cessation) and the intervention (Sister-to-Sister). In mediator analyses, it is posited that variation in a given independent variable (intervention) accounts for variation in the mediators (self-efficacy, spiritual well-being, social support, cessation resources) and variations in mediators account for variations in outcome (6-and 12-month cessation). For these analyses, we will follow the methods of Baron and Kenney [149], Holmbeck [150], and Kraemer [151]. GLMM analyses as outlined above will evaluate the relationship between the outcome (6- and 12-month cessation) and the intervention (Aim 1). Next, the relationship between intervention and the putative mediator variables (self-efficacy, spiritual well-being, social support, cessation resources) will be evaluated as described for Hypothesis 2.1. Finally, the mediating effect of self-efficacy, spiritual well-being, social support, cessation resources on a significant treatment effect will be evaluated in a GLMM model that simultaneously regresses treatment (TX vs C) and the putative mediating variables on outcome (smoking cessation). A significant smoking cessation/treatment relationship that becomes nonsignificant following the addition of the putative mediator covariable suggests that the latter accounts for (mediates) the former observed relationship. For example, we conclude that the relationship between treatment and smoking cessation is mediated by self efficacy if the variable representing self efficacy is significant and a previously significant treatment effect becomes nonsignificant in the multivariable model containing both.

102,10:1513-1684.

144. Little RJA, Rubin DB (1987) *Statistical Analysis with Missing Data*. 1987. J. Wiley & Sons, New York.

145. Little RJA, Rubin DB (1987) *Statistical Analysis with Missing Data*. 1987. J. Wiley & Sons, New York.

146. Gibbons R. *Longitudinal Data Analysis*. 2006. John Wiley and Sons, Inc. New York.

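### The adjusted Hypothesis 2.1 models can condition on follow-up values of the other outcome factors, so the adjusted treatment effect on a factor can be substantially attenuated or take the wrong sign

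*SAP*

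**What the plan says.** Under Analyses for Secondary Aims, Hypothesis 2.1 states that women receiving the intervention "will have greater improvement in individual factors (self-efficacy, spiritual well-being"), and also in social support and cessation resources. For the analysis, "each of the individual variables within the factors will be used individually as the outcome (dependent) variables in the GLMM". The model described first has treatment and measurement time as fixed effects, neighborhood as a random effect and a fixed intercept for each neighborhood pair. An adjusted version follows: "Additional covariates, as described above, will be added to the model to determine the effect of treatment on these outcomes", with nothing further on which covariates are meant.

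The covariate list for adjusted models stands under Analyses for Primary Aim. It runs from demographic variables through nicotine dependence, depression, body mass index, stress and neighborhood measures, and ends with "time dependent covariates of self efficacy, spiritual well-being, social support, and" cessation resources. Selection works as follows: "Each covariate considered for inclusion will be examined individually for a relationship with cessation outcomes"; then "those variables with a p value < .25 will be included in an initial model"; then backward elimination, in which a variable is dropped on this condition: "If the removal of the potential confounder variable does not result in a significant reduction in model fit".

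The Hypothesis 2.1 text does not remove the modelled factor or the other three from that list, does not restrict them to baseline values, and does not name a new screening target.

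**The concern.** The list was written for a cessation outcome. Carried over to a factor outcome, it offers each of the four Hypothesis 2.1 outcomes as a covariate for the others and, nominally, for itself. Because they are labelled time-dependent, their follow-up values are meant, and those are measured after randomisation and may be changed by treatment.

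This changes the question. Hypothesis 2.1 asks whether the intervention improves a factor. A model that holds the other three at their follow-up values asks whether the factor improves beyond what goes with improvement in the others. Improvement shared across correlated factors is then partly subtracted. A factor that treatment leaves unchanged can appear to worsen.

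The plan's own expectations make entry plausible. Hypothesis 2.1 expects treatment to move the factors, and the mediation section posits that "variations in mediators account for variations in outcome (6-and 12-month cessation"). Variables related to cessation are the ones that a screen against cessation lets through.

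The mediation analysis also takes its treatment-to-mediator step from Hypothesis 2.1 without saying whether the adjusted or the unadjusted model is meant, so the ambiguity could carry into Hypothesis 2.2.

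**Working it through.** The SAP gives no effect size, SD, correlation or power for the factors, so there is no figure to reproduce. All numerical inputs below are assumptions, except the p < .25 screen, which is from the SAP.

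**1. All three other factors in the model.** Assume one visit, unit within-arm SD, equal within-arm correlation r among the four factors, and a treatment effect d on each. Regressing one factor on the other three gives each a partial slope of r/(1+2r). The adjusted effect is

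d − 3 × [r/(1+2r)] × d = d × (1−r)/(1+2r).

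If the modelled factor has no true effect and the other three each move by d, the adjusted effect is −3rd/(1+2r). With d = 0.30 SD:

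| r | Share retained (1−r)/(1+2r) | 0.30 SD becomes | Factor with no true effect shows |
|---|---|---|---|
| 0 | 1.00/1.0 = 100% | 0.30 | 0 |
| 0.1 | 0.90/1.2 = 75% | 0.225 | −0.075 |
| 0.3 | 0.70/1.6 = 44% | 0.131 | −0.169 |
| 0.5 | 0.50/2.0 = 25% | 0.075 | −0.225 |

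If treatment does not move the other three factors, the effect stays at 0.30 whatever r is.

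**2. Selection applied.** The covariates are only candidates, so the selection procedure was simulated: the p < .25 screen against cessation, then likelihood-ratio backward elimination. The SAP states no level for the elimination step; 0.05 was assumed. Other assumptions were d = 0.30 SD on every factor, r = 0.1, 0.3 or 0.5, total N of 200 or 400, a base quit rate of 12%, one visit, no clustering and 200 replicates per scenario. All four factors were candidates. The modelled factor was then removed, so that only the other three could act as covariates. Ranges are over r and N:

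| Odds ratio of cessation per SD of factor | Unadjusted effect | Adjusted effect | Runs in which the modelled factor itself survived selection |
|---|---|---|---|
| 1.0 | 0.28–0.30 | 0.27–0.29 | 5–8% |
| 1.2 | 0.29–0.30 | 0.16–0.28 | 18–29% |
| 1.5 | 0.29–0.32 | 0.10–0.24 | 56–84% |

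The distortion is almost nil when the factors are unrelated to cessation. It grows with that relationship and with r.

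**3. The factor as its own covariate.** If the same-visit value of the outcome is entered as a covariate, its coefficient is 1 and the treatment coefficient is 0. A least-squares fit confirmed this to machine precision.

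**4. Without the post-baseline factors.** The unadjusted column shows the effect staying at 0.28–0.32 against the assumed 0.30.

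**The case against.** The cross-reference may not point only to the longer list. Preliminary Analysis, also earlier in the SAP, names age, income, education, nicotine dependence and depression as variables to investigate when identifying covariates for later analyses. That ambiguity is real, but it does not clear the plan. The list under Analyses for Primary Aim is the nearer antecedent, matches the wording of the adjusted step more closely, and already contains those five variables.

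A reader might infer that the adjusted effect on every factor is removed or badly distorted. The documents do not support that. The factors are candidates that must survive selection, and under some assumptions the loss is close to zero. Complete removal requires a factor to be entered as a covariate for itself, which is the literal reading but one that few analysts would carry out. The narrower problem needs no such reading: an analyst who drops only the outcome itself may still condition on the other three.

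Screening against cessation is likewise the literal reading. One could argue that the procedure carries over with the modelled factor as the target. The SAP does not say so, and changing the target would not remove the post-baseline factors from the candidate list.

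A reader might also turn the retained percentages into a loss of power. That step is not supported. The SAP names the treatment-by-time interaction as the test of primary interest, in a model with neighborhood effects, whereas the calculation concerns a group difference at one visit without clustering.

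Finally, removing the four factors from the Primary Aim list would carry over to Hypothesis 2.1 through the cross-reference. That is true, but it would leave the screening target unclear.

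**Conclusion.** The point holds in a limited form. A stated rule, not merely an omission, allows the adjusted Hypothesis 2.1 models to condition on variables that the hypothesis says treatment changes. The adjusted estimate can then answer a different question and be substantially attenuated, or be negative for a factor with no true effect.

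The size is uncertain. With all three other factors in the model, retention runs from 100% at r = 0 to 25% at r = 0.5, assuming equal effects and equal correlation. With selection applied, an assumed 0.30 SD fell to between 0.10 and 0.29 across the scenarios tried. None of these correlations, effects or odds ratios comes from the SAP.

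The reach is also limited. This is a secondary aim, and the model without added covariates, which addresses Hypothesis 2.1 directly, is untouched. The change should still be made, because the SAP gives no rule for reconciling adjusted and unadjusted results that disagree.

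**What to change.** Replace the cross-reference with a covariate statement specific to Hypothesis 2.1:

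- Adjusted models use baseline covariates only, namely the baseline values of the covariates listed under Analyses for Primary Aim, including the baseline value of the factor being modelled.
- No post-baseline value of self-efficacy, spiritual well-being, social support or cessation resources enters as a covariate.
- Covariates are not selected by their association with cessation.
- Follow-up values of the four factors are used as predictors only in the Hypothesis 2.2 mediation analysis.

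Including the factor's own baseline value suits a hypothesis about improvement, because measurement time in the model covers only 6 and 12 months. The cost is a short change to the SAP text and slightly less explained variance in the adjusted models. It should need no new data, on the assumption that the listed covariates and the four factors are measured at baseline.

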Study Title:
**Social Ecological Based Smoking Cessation Intervention in Public Housing
Neighborhoods**

R01HL090951

Date: 8/09/2018

Statistical Analyses.

Preliminary Analysis. Univariate descriptive statistics and frequency distributions will be calculated as appropriate for all variables. These analyses will identify departures from distributional assumptions for proposed procedures. If departures are identified, appropriate transformations of data will be applied, or alternative analysis procedures (e.g., semi-parametric or nonparametric) will be employed. Baseline values for demographic and other putative prognostic variables will be compared for imbalance across the two treatment conditions (TX, C). These analyses will identify potential confounding variables to be used as covariates in subsequent analyses. Putative prognostic variables that will be investigated through these descriptive analyses include age, income, education, nicotine dependence score, and depression score. *To investigate potential limits on generalizability, we will compare demographic and other baseline characteristics of the dropouts with those who were completers.*

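### The Hypothesis 2.2 mediation model specifies neither the baseline value of each factor nor a fixed set of baseline prognostic variables, so the factor-to-cessation slope is open to confounding

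*SAP*

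**What the plan says.** All references are to the SAP.

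- **Hypothesis 2.2** is worded in terms of change: "Positive changes in individual factors (self-efficacy, spiritual well-being), interpersonal factors", and so on through the four factors, are to mediate the cessation effect.
- **The mediator analysis** has three steps: treatment to cessation (Aim 1); then "the relationship between intervention and the putative mediator variables", run as for Hypothesis 2.1; then a joint model, "evaluated in a GLMM model that simultaneously regresses treatment (TX vs C) and the putative mediating variables on outcome (smoking cessation"). Its worked example concludes mediation when the factor is significant and a "previously significant treatment effect becomes nonsignificant in the multivariable model containing both".
- **Model structure.** "A generalized linear mixed models (GLMM) approach, as described for the Primary Aim, will be used for Aim 2". This brings in measurement time, a random neighborhood effect and a fixed intercept per neighborhood pair.
- **Covariates** are mentioned in three other places. Preliminary Analysis compares the arms for baseline imbalance: "These analyses will identify potential confounding variables to be used as covariates in subsequent analyses". The variables it names are these: "Putative prognostic variables that will be investigated through these descriptive analyses include age, income, education, nicotine dependence score, and depression score". The primary-aim section selects covariates by a univariate p-value screen and backward elimination; there the four factors are candidates only as time-dependent covariates. For Hypothesis 2.1, "Additional covariates, as described above, will be added to the model to determine the effect of treatment on these outcomes"; the outcomes meant are the factors, not cessation.

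The text on the joint model mentions no baseline factor value and no covariate, and does not say whether a factor enters as a follow-up level or as a change.

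**The concern.** Randomization, here of neighborhoods, protects the comparison of the arms on the factors and on cessation. It does not protect the slope of cessation on a factor within an arm, which is an observational association. A woman who is more confident, less dependent or less depressed at the start may both score higher on the factor later and be more likely to quit. The factor's coefficient then partly measures where she started.

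If treatment also moves the factor, as Hypothesis 2.1 expects, this biased slope combines with a real treatment-to-factor effect and produces an apparent indirect effect where there may be none. Aim 2's account of why the intervention works rests on this step. The primary cessation comparison is not affected. Correct time order of factor and outcome, or a confidence interval for the indirect effect, would not remove the bias.

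**Working it through.** **1. Does another section supply the missing terms?**

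- *Preliminary Analysis* selects on imbalance between arms. Confounding of factor and cessation exists when the arms are perfectly balanced, so this screen does not look for it.
- *The primary-aim covariate step*, if it carries over, could bring in age, income, education, nicotine dependence and depression. It can also drop any of them on a p-value. Its list has the factors only as time-dependent covariates, which are the mediators themselves.
- *The Hypothesis 2.1 covariates* belong to models with the factors as outcomes.

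No section supplies the baseline factor values.

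**2. Direction of the bias.** The SAP states no sample size, quit rate or effect, so there is no figure of its own to reproduce. Write the follow-up factor as M = a·T + ρ·M0 + error, with M0 its baseline value (variance 1) and M having no effect on quitting. Within an arm:

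- level: Cov(M, M0) = ρ; for ρ = 0.6 this is +0.6;
- change: Cov(M − M0, M0) = ρ − 1; for ρ = 0.6 this is −0.4.

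If M0 predicts quitting, the inert level picks up a positive slope and the inert change score a negative one. With M0 in the model both are removed.

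**3. Size of the slope (all inputs assumed).** 420 women; an inert factor that treatment raises by 0.5; baseline factor and nicotine dependence both allowed to predict quitting, the baseline factor with a log-odds ratio of 0 to 0.5 per SD. Odds ratio for the factor (true value 1.00):

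| Model | Odds ratio |
|---|---|
| Follow-up level, no baseline terms | 1.07–1.43 |
| Level plus nicotine dependence | 1.00–1.33 |
| Raw change score | 0.75–0.93 |
| Baseline factor and nicotine dependence included | about 1.00 |

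Adjusting for dependence alone is not enough when the baseline factor itself predicts quitting.

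**4. How often the planned sequence would declare mediation (level reading, all inputs assumed).** 2,000 runs per setting, ordinary logistic regression without clusters, two-sided 0.05. Logit of quitting = −2.3 + 0.8·T + 1.0·U, with U a standard normal baseline trait (control quit rate about 12%). Follow-up factor = a·T + 0.7·U + noise (SD 0.7); measured baseline = U + noise (SD 0.3). Percentages are of runs with a significant treatment effect and require every planned step, including treatment to factor.

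| Shift a | N | As written | With baseline factor |
|---|---|---|---|
| 0.5 | 250 / 400 / 800 | 63 / 58 / 44% | 4 / 3 / 2% |
| 0.3 | 250 / 400 / 800 | 31 / 30 / 18% | 2 / 1 / 1% |
| 0 | 250 / 400 / 800 | 1.0 / 0.5 / 0.0% | 0.1% or less |

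These inputs make the trait a strong predictor of quitting. With weaker ones (420 women, about 15% quitting, log-odds ratios per SD of 0 to 0.5 for the baseline factor and −0.3 to −0.5 for dependence), the SAP's rule declared mediation in 4–47% as written and about 1% with both baselines added.

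Two cautions apply. The declaration rates also reflect the loss-of-significance rule: they fall as N grows although the confounding is the same, so the odds ratios in step 3 are the cleaner measure. And a baseline measured with error (reliability here 1/(1 + 0.3²) = 0.92) leaves a remnant: at N = 800 the inert factor still passed the treatment and treatment-to-factor tests and was significant in about 13% of runs with a significant treatment effect.

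**The case against.** **The model is not bare.** A reader might infer that it contains only treatment and the factors. The SAP does not support that: the primary-aim GLMM applies to all of Aim 2, so time, neighborhood and pair terms are in, and the primary-aim covariate step arguably comes too. The wording about a model containing both belongs to an example of the decision rule and is not a list of terms. This stands. But none of the inherited structural terms deals with differences between women, and the covariate step neither lists the baseline factor values nor guarantees the prognostic variables.

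**A mere marker would not usually pass.** A reader might also infer that any factor marking women likely to quit will be reported as a mediator. The plan also examines treatment to factor and requires loss of treatment significance; with no shift in the factor, the full sequence declared mediation in 1% of runs or fewer. This stands: the error needs a factor that treatment moves and that shares a baseline cause with quitting, and even then it may occur rather than must.

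**Level or change is not stated.** The SAP cannot be said to use the level. This stands, but both readings are biased, in opposite directions.

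**The figures are assumptions**, and the simulations treat one factor, whereas the SAP enters the mediators together. This stands. The mechanism also fits self-efficacy better than cessation resources, which the SAP classes as a neighborhood factor.

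**Conclusion.** The point holds as an under-specification of a secondary, explanatory analysis. Followed as written, the joint model leaves the non-randomized factor-to-cessation slope unadjusted for where each woman started, and no other section repairs this.

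The direction follows from the algebra whenever the follow-up factor carries part of its baseline (ρ between 0 and 1) and that baseline, or a correlate of it, predicts quitting. The size does not: the odds ratios and declaration rates above are illustrations from assumed inputs, and with no link between the baseline factor and quitting the bias is slight (1.07 at the low end). Baseline adjustment would not cure reverse causation if factor and cessation are measured at the same visit; that is a separate matter. This is a cheap improvement to the plan. It does not touch the primary analysis.

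**What to change.** In the Hypothesis 2.2 text, state that:

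- both cessation models, without and with the factors, include as fixed covariates the baseline value of each factor entered and the five variables named under Preliminary Analysis (age, income, education, nicotine dependence, depression), kept whatever their p-values, so that the two treatment effects are compared on the same adjustment;
- each factor enters in a stated form (follow-up level or change), with its baseline value alongside in either case;
- the factor-to-cessation path is observational, with a sensitivity analysis showing how strong an unmeasured common cause would have to be to remove the indirect effect.

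**Cost.** Mainly wording: Hypothesis 2.1 speaks of improvement, which implies that baseline factor values are collected. The price is parameters. At an assumed 420 women and 15% quitting there are 420 × 0.15 = 63 quitters at a time point. Treatment, four factors, four baselines and five covariates make 14 terms before time and pair intercepts, or 63/14 = 4.5 quitters per term. Fitting one factor with its own baseline at a time gives 1 + 1 + 1 + 5 = 8 terms, or 63/8 = 7.9 per term. The SAP should say which it will do; single-factor models answer a narrower question, since they do not adjust for the other factors.

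### Hypothesis 2.2 infers mediation from a treatment effect losing significance and writes no indirect effect or interval, so true partial mediation can go undeclared

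*SAP*

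**What the plan says.** Aim #2, under Analyses for Secondary Aims, sets out "to determine if these factors mediate the effect of treatment on smoking cessation outcomes". Four factors are named: self-efficacy, spiritual well-being, social support and cessation resources. Neither the aim nor Hypothesis 2.2 asks for complete mediation.

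The text for Hypothesis 2.2 has three steps: the Aim 1 model of treatment on cessation, the Hypothesis 2.1 models of treatment on each factor, and a final model with treatment and mediators together. One general sentence says that a treatment effect which loses significance when the mediator is added suggests mediation. The worked example turns this into a rule: the relationship is "mediated by self efficacy if the variable representing self efficacy is significant and a previously significant treatment effect becomes nonsignificant in the multivariable model".

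Two further details matter.
- The final step looks at the mediating effect "on a significant treatment effect will be evaluated in a GLMM model that simultaneously regresses treatment (TX vs C) and the putative mediating variables". It is thus limited to a significant treatment effect, and it speaks of several mediators at once.
- The worked example speaks of an effect that is "nonsignificant in the multivariable model containing both", which reads as treatment plus a single mediator.

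The Aim 2 models carry a neighborhood random effect and a "pair-specific fixed intercept parameter". The 95% intervals planned under Analyses for Primary Aim are for intervention effect sizes, with cessation differences and odds ratios as examples. None is written for a mediated effect. The SAP cites three method papers on mediation but adopts no other test from them in its own text.

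**The concern.** Comparing a significant p-value before adjustment with a nonsignificant one after it is not a test of the change between the two coefficients. An effect near the threshold can cross it after a trivial change. A strong effect can fall by half and stay significant. In the second situation the SAP's text gives no way to conclude mediation, even when treatment clearly moves the factor and the factor clearly predicts cessation.

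With four mediators at individual, interpersonal and neighborhood level, each may carry only part of the effect. A factor that does so could be reported as not mediating merely because treatment also works in other ways, and the reader would get neither the size nor the precision of the mediated part. The unclear entry of the mediators adds to this, because the two readings can give opposite answers from the same data.

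**Working it through.** The SAP states no sample size, number of pairs, alpha, quit rate, intraclass correlation or mediator effect. There is no plan figure to reproduce, and every percentage below is an illustration.

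**Inputs.** The model form is the SAP's: a logistic mixed model with pair-specific fixed intercepts and a random neighborhood intercept. The rest is assumed:
- 25 women per neighborhood, so 8, 12 and 24 pairs give 8×25 = 200, 12×25 = 300 and 24×25 = 600 women per arm;
- intraclass correlation 0.02, 10% control quit rate, alpha 0.05;
- independent mediators that vary between women;
- a treatment main effect at one time point, tested on t with pairs minus 1 degrees of freedom (Laplace fit).

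There were 600, 600 and 400 runs, so the simulation standard error at 50% is √(0.25/600) = 2.0 points, or √(0.25/400) = 2.5 points at 24 pairs.

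**Formulas.** Indirect effect = a×b, with a the treatment-mediator coefficient (SD) and b the mediator-cessation coefficient (log-odds per SD). Effect left after adjustment ≈ total minus the a×b of the mediators in the model. This is approximate, because log-odds from nested logistic models are not exactly additive.
- Case 1, one mediator: 0.5×0.8 = 0.40, direct 0.405. Share 0.40/0.805 = 50%; 0.405 is left.
- Case 2, four equal mediators, no other path: 0.4×0.5 = 0.20 each, 0.80 in all. Share 25% each; 0.60 is left one at a time, 0 jointly.
- Case 3, as case 2 plus an outside path of 0.40: total 1.20. Share 0.20/1.20 = 17% each; 1.00 is left one at a time, 0.40 jointly.

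**Rule as coded:** treatment effect, treatment-mediator path and mediator all significant, adjusted treatment effect nonsignificant. **Comparator:** treatment effect significant and the 95% Monte Carlo interval for a×b excludes zero.

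Detection of a given true mediator:

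| Case | Method | 8 pairs | 12 pairs | 24 pairs |
|---|---|---|---|---|
| 1 | Rule | 36% | 55% | 47% |
| 1 | Interval | 47% | 80% | 97% |
| 2 | Rule, one at a time | 16% | 22% | 14% |
| 2 | Rule, jointly | 35% | 66% | 92% |
| 2 | Interval | 35% | 69% | 97% |
| 3 | Rule, one at a time | 13% | 4% | under 1% |
| 3 | Rule, jointly | 57% | 69% | 44% |
| 3 | Interval | 63% | 93% | 100% |

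**Source of the gap.** In case 1, the runs with treatment effect and both paths significant, blocked only by a still-significant direct effect, were 11%, 25% and 50%. Adding these to the rule gives 36+11 = 47, 55+25 = 80 and 47+50 = 97, which is the interval row.

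**Growth with sample size.** Without clustering (1,000 runs), the rule at 200, 300, 600 and 1,600 per arm gave:
- case 1: 50%, 54%, 37%, 4%;
- case 2: 22%, 26%, 11%, under 1% one at a time; 60%, 84%, 94%, 95% jointly;
- case 3: 7%, 2%, 0%, 0% one at a time; 66%, 65%, 43%, 6% jointly.

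The interval reached 100% in all three cases at 1,600. A repeat of case 1 gave 46%, 55%, 35% and 4% for the rule against 72%, 91%, 100% and 100% for the interval. The clustered runs were not repeated. Any nonzero remainder eventually becomes significant. Only case 2 entered jointly leaves nothing, and its ceiling is 1 − 0.05 = 95%.

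**Other inputs.** With a×b = 0.4×0.6 = 0.24 and direct 0.5 (share 0.24/0.74 = 32%), about 8% quitting in controls at mediator zero and no clustering, the rule gave 22%, 32%, 28% and 11% at 150, 250, 400 and 800 per arm.

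**False positives** for a mediator that treatment does not move: rule under 1% one at a time, about 3–4% jointly if the other three mediate; interval 1–6%.

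**The case against.** **The wording is softer than a prohibition.** A reader might infer that the SAP forbids declaring partial mediation. It does not say so: the general sentence says suggests, the example says if, and three cited papers that cannot be seen here may offer other tests. That stands as a limit on wording. It does not cure the defect, because the criterion written out is the only one an analyst can follow from the text, and it is silent on an effect that shrinks but stays significant.

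**The requirement of a significant treatment effect can cost more.** In case 1 at 8 pairs, dropping it moves the interval from 47% to 94% (47 points), whereas dropping the nonsignificance rule moves 36% to 47% (11 points). At 12 pairs the comparison turns: from 80% to over 99% (about 20 points) against 55% to 80% (25 points). This stands, so indirect effects should be reported whether or not that requirement is met.

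**Which treatment effect?** Analyses for Primary Aim makes the treatment x time interaction the test of primary interest, and the mediation steps refer back to Aim 1. The simulations use a main effect at one time point. If the interaction is meant, the percentages do not apply. This stands too.

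**The interval is not safe in general.** A reader might infer that the change costs only a nominal 5% false-positive rate. That holds only without reverse causation or mediator-outcome confounding, and the mediation text fixes no time order. Without clustering, assume a direct effect of 0.8 log-odds, treatment raising the mediator by 0.4 SD, quitting raising it by 0.5 SD and no mediator effect on cessation. False mediation at 200, 300 and 600 per arm was then 27%, 22% and 6% by the rule against 72%, 92% and 100% by the interval; a repeat gave 29%, 25%, 7% against 76%, 91%, 100%. With an unmeasured common cause instead, it was 7%, 4%, 1% against 23%, 33%, 71%. Both mislead, and the interval more often.

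**Joint entry shrinks the loss.** In case 2 it is 0, 3 and 5 points (35−35, 69−66, 97−92). This is correct, but the SAP does not settle on joint entry.

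**Conclusion.** The point holds in this form: the one criterion written for Hypothesis 2.2 does not test the change in the treatment effect, gives no estimate of the mediated part, and can leave true partial mediation undeclared. That follows from the text alone. So does the worsening with sample size wherever a material path runs outside the mediators in the model.

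The size depends on assumptions. The loss is large if mediators enter one at a time (case 2 at 24 pairs: 14% against 97%) and small if all four enter jointly with little effect outside them (92% against 97%). The percentages must not be read as this trial's power. They rest on assumed pairs, quit rate, clustering and paths, a main effect at one time point, and mediators that vary between women. Cessation resources, which the SAP calls a neighborhood factor, is not covered if measured per neighborhood.

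Only secondary Aim 2 is affected; Aim 1 is not. The change should be made, but it is not critical to the trial's main conclusion.

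**What to change.** Replace the loss-of-significance rule with text along these lines:

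> For each mediator, the indirect effect (treatment-mediator coefficient times mediator-cessation coefficient, log-odds scale) will be estimated from the paired-neighborhood mixed models with a 95% Monte Carlo confidence interval, and reported with the direct effect and its interval. Mediation is concluded if the indirect-effect interval excludes zero; a nonsignificant direct effect is not required. The four mediators enter one cessation model together; one-at-a-time models are supportive. Results are exploratory, without multiplicity control.

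Three additions are needed.
- If the condition of a significant treatment effect is kept, name it as the treatment contrast at the given time point, not the treatment x time interaction, and report indirect effects whether or not it is met.
- Where the data allow, use a mediator measured before the outcome, for example the 6-month mediator with 12-month cessation, and call same-visit results associational.
- State at which level cessation resources is measured. If per neighborhood, expect a wide interval.

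The cost is SAP wording and modest programming on data already planned. Without reverse causation or confounding, the false-positive rate per mediator rises from under 1% (one at a time) to about 5%. With four null mediators, the chance of at least one false positive at one time point was 5%, 8% and 21% at 8, 12 and 24 pairs, hence the exploratory label. A confirmatory claim over four mediators and two time points would need 1 − 0.05/8 = 99.375% intervals. In case 2 that takes detection from 35%, 69%, 97% to 12%, 46%, 97%.
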